#### 8. SAMPLE SIZE JUSTIFICATION

It is assumed that change in AAPS from Main Study baseline to Week 12 will be normally distributed with a standard deviation (SD) of 1.9. Assuming a 1:1:1:1 randomization, 240 subjects (60 per treatment group) is sufficient to achieve at least 80% power to detect a treatment effect of 1.0 between each of the olorinab treatment groups and placebo by a 2-sample t-test using a 2-sided significance level of 0.05. Note, under the same assumptions there is at least 95% power to detect a treatment effect of 1.0 between the pooled olorinab treatment group (180 subjects) and placebo (60 subjects).

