#### 9.2. MULTICENTER STUDIES

This study will be conducted by multiple investigators at multiple investigational sites within the United States. Randomization to treatment arms is not stratified by center. Randomization to treatment arms is stratified by sex (male, female) and IBS subtype (IBS-C, IBS-D). Data from all sites will be pooled and statistical analyses will not be adjusted for investigational site or geographic region. Ad-hoc analyses may be conducted by site or by pooling sites.

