- IBS subtype) as factors and baseline AAPS as a covariate will be run for each of the 100 datasets to obtain 100 estimators of interest.
- ✓ Step 4: SAS PROC MIANALYZE will be used to produce overall pooled estimates (mean of 100 estimates) of least squares mean differences between placebo and each treatment with associated standard errors, CIs, and pooled p-values presented. Additionally, SAS PROC MIANALYZE will be used to produce p-values for within-treatment group change based on a one sample t-test using pooled least squares mean estimates and associated standard errors. Summary statistics presented for Week 12 records will be based on the mean of the imputed records per subject per time point.

The missing AAPS values will be imputed first and change from baseline values will be calculated based on imputed AAPS scores.

There could be certain adjustments to the MI model specified in Step 2 above due to unexpected data issues after unblinding treatment. All post-unblinding modifications to the MI model or approaches to address missing data will be described in the Clinical Study Report (CSR).

• Nonparametric Wilcoxon Rank-Sum Test: The Wilcoxon Rank-Sum Test will be used to compare change in AAPS at Week 12 between treatment (each dose of olorinab vs placebo, olorinab 25 and 50 mg pooled versus placebo, and pooled olorinab vs placebo).

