## 18.2.4. SENSITIVITY ANALYSIS OF SECONDARY AND KEY EXPLORATORY EFFICACY VARIABLES

The robustness of the secondary endpoints' results will be assessed using various sensitivity analyses. The following analyses will be used:

- For continuous endpoints, the ANCOVA with OC, ANCOVA with MI, and Non-parametric Wilcoxon Rank-Sum Test will be implemented as described in Section 18.1.4.
- For binary endpoints based on AAPS and bowel motility endpoints (including the three composite responder endpoints for IBS-C and IBS-D), the sensitivity to missing data assumptions will be evaluated with the following models:
  - CMH with OC: The CMH test described in the analysis of secondary efficacy variables Section will be repeated on the population of subjects with observed data for the given analysis.
  - o CMH with NRI (non-responder imputation): The CMH test described in the analysis of secondary efficacy analysis Section will be completed on all subjects in the FAS. Subjects will be considered a non-responder if they do not meet the endpoint criteria (e.g. a ≥ 30% improvement in AAPS) or are missing data at the time point of interest. All non-responders at the time point of interest, as well as subjects who discontinue study treatment at any time prior to that time point for any reason, will be defined as non-responders for the analysis. Randomized subjects without at least 1 post-baseline observation will also be defined as non-responders in NRI analyses.
  - o Logistic regression (OC): A logistic regression model using observed cases will be used to analyze treatment comparisons between the proportion of subjects achieving a ≥ 30% improvement in AAPS from baseline to the given time point, with the explanatory variable of treatment (placebo, olorinab 10 mg, olorinab 25 mg, olorinab 50 mg), randomization stratification factor (sex and IBS subtype) and baseline AAPS as a covariate. In addition, two additional logistic regression models will be completed with the following treatment groupings: 1) placebo, olorinab 10 mg, and olorinab 25 and 50 mg pooled and 2) placebo and pooled olorinab. The endpoint of subjects

[figure not shown]

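### The Wilcoxon sensitivity test drops both the randomization strata and the baseline covariate, so a disagreement with the MMRM cannot be cleanly explained; a stratified rank ANCOVA would serve better

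*SAP*

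**What the plan says.** SAP 9.2 records that "Randomization to treatment arms is stratified by sex (male, female) and IBS subtype (IBS-C, IBS-D". The primary MMRM and the by-visit MMRM (SAP 18.1.3), the observed-case ANCOVA and the multiple-imputation ANCOVA (both 18.1.4) all include these two factors and baseline AAPS.

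The third sensitivity analysis in 18.1.4 is different: "The Wilcoxon Rank-Sum Test will be used to compare change in AAPS at Week 12 between treatment". It is applied to each dose, to the pooled 25 and 50 mg groups, and to all olorinab pooled, each against placebo. No stratification and no covariate is named. SAP 18.2.4 extends it to the continuous secondary endpoints ("Non-parametric Wilcoxon Rank-Sum Test will be implemented as described in Section 18.1.4"), and 18.1.5 repeats it in the Per Protocol Set.

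**The concern.** A sensitivity analysis is easiest to read when it changes one assumption at a time. This one relaxes normality and, in the same step, removes the adjustment that every other model carries. Suppose the MMRM is significant and the rank test is not. The cause could be outliers or skewness in AAPS, or simply the lost adjustment. The observed-case ANCOVA does not bridge the gap, because moving from it to the rank test still changes both things.

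The second issue is calibration. Stratified randomization removes between-stratum variation from the treatment contrast, but an unstratified test still counts that variation in its null variance. If the strata predict change in pain, the p-values are somewhat too large. What is at stake is how robustness is reported: a true effect could be described as not robust for a reason unrelated to the shape of the data.

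**Working it through.** **Inputs from SAP section 8.** The endpoint is assumed normal with SD 1.9 ("It is assumed that change in AAPS from Main Study baseline to Week 12 will be normally" "distributed with a standard deviation (SD) of 1.9"). The effect is 1.0 ("to detect a treatment effect of 1.0 between each of the olorinab treatment groups and placebo"), with 60 per arm ("Assuming a 1:1:1:1 randomization, 240 subjects (60 per treatment group) is sufficient to achieve at least 80% power") and a "2-sample t-test using a 2-sided significance level of 0.05".

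**Assumed, because the documents are silent.** Share of variance in change explained by the strata and by baseline AAPS: 0-20% each. About 75% female, subtypes about equal, strata balanced between arms, complete data.

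**1. The plan's own power figure.** The standardized effect is 1.0 / (1.9 × √(2/60)) = 1.0 / 0.347 = 2.88. By normal approximation, power is Φ(2.88 − 1.96) = 82.2%; by noncentral t it is 81.6%. The stated figure of at least 80% is reproduced.

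**2. Cost of using ranks when nothing is prognostic.** The rank-sum test has relative efficiency 3/π = 0.955 under normality, so 60 per arm acts like 60 × 0.955 = 57.3. Power is 79.8% (79.9% simulated). Ranks alone cost about 2 points.

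**3. Level.** With balanced strata explaining a share R² of the variance, the unstratified statistic has null variance of about 1 − R². Its actual two-sided level is then about 2 × [1 − Φ(1.96 / √(1 − R²))].

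| Strata R² | 1.96 / √(1 − R²) | Level by formula | Wilcoxon, simulated | van Elteren, simulated |
|---|---|---|---|---|
| 0% | 1.960 | 5.0% | 5.0% | 5.2% |
| 5% | 2.011 | 4.4% | 4.3% | 5.1% |
| 10% | 2.066 | 3.9% | 3.8% | 5.0% |
| 20% | 2.191 | 2.8% | 2.8% | 4.8% |

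(Normal data, 8,000 runs per cell.) Allowing for repeat simulations, the level is roughly 3.7-4.5% at strata R² of 5-10%. With heavy-tailed or skewed residuals it can fall to about 3%.

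With non-prognostic strata and baseline R² of 10% or 20%, the simulated Wilcoxon level is 4.9%. Baseline is not balanced by design, so its chance imbalance is correctly part of the null variance. Omitting it does not make the test conservative.

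**4. Power against the natural replacement.** The comparison is 60 v 60 with effect 1.0, total SD 1.9 and 6,000 runs per cell (Monte Carlo SE at 80% power: √(0.8 × 0.2 / 6,000) = 0.5 points).

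| Residuals | Strata R² + baseline R² | Wilcoxon | van Elteren | Stratified rank ANCOVA | Rank ANCOVA minus Wilcoxon |
|---|---|---|---|---|---|
| Normal | 5% + 10% | 80.3% | 80.6% | 84.0% | 3.7 |
| Normal | 10% + 12% | 81.1% | 83.2% | 87.3% | 6.2 |
| t(3) | 5% + 10% | 94.2% | 95.0% | 97.3% | 3.1 |
| t(3) | 10% + 12% | 93.0% | 95.4% | 98.2% | 5.2 |
| Skewed | 5% + 10% | 93.8% | 95.3% | 97.4% | 3.6 |
| Skewed | 10% + 12% | 92.1% | 94.8% | 97.3% | 5.2 |

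Rank ANCOVA type I error in these settings was 4.2-5.3%. With no prognostic covariate, rank ANCOVA lost power, for example 80.1% v 78.2% with normal data. Across repeat simulations the loss was about 1-3 points, and smaller in some cells.

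**The case against.** Much of the opposing case stands, and it limits the point.

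- **Weaker than the model it checks.** A reader might infer this, but it holds only under normality. With strata R² 5% and baseline R² 10%, Wilcoxon power was 94.5% against 88.2% for ANCOVA (standing in for the Week 12 MMRM contrast) with t(3) residuals, and 93.8% against 86.6% with skewed residuals. With no covariate effects the figures were 97.3% v 85.1% and 97.7% v 81.7%. ANCOVA led under non-normality only at strata 10% plus baseline 20%, by 1.4 and 2.1 points. This does not defend the planned test against another rank test, which is the comparison that matters for the fix.
- **Conservative because baseline is dropped.** This is also tempting, but wrong: only prognostic strata lower the level.
- **Ignores baseline.** Too strong. The test is on change, which subtracts baseline (SAP 7.6); what is missing is adjustment for baseline as a covariate.
- **A disagreement would be uninterpretable.** Overstated. The MMRM and ANCOVA estimate the stratum and baseline effects, and SAP 9.5 lists subgroups by sex, subtype, their combination and baseline AAPS. A reader can judge whether lost adjustment is plausible, but cannot separate the two causes.
- **No other safeguard against non-normality.** Not so: protocol 8.3 provides for alternatives, including non-parametric analysis and log transformation, where assumptions fail.
- **A decision depends on it.** None does. SAP 18.1.3 ties success to four MMRM tests, two adjusted sensitivity analyses exist, and SAP 9.4 treats the comparisons as exploratory.

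The minimal fix also gains little. Van Elteren added between 0.3 and 2.1 points under normality in the table above, and loses 1.2 points (79.9% to 78.7%) if nothing is prognostic.

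**Conclusion.** The point holds as a small, cheap improvement. The planned rank test differs from every other treatment-comparison model for this endpoint in two respects at once, which blurs what it can show. It is mildly conservative if, and only as far as, sex and IBS subtype predict change in AAPS. It gives up roughly 3-6 power points against a stratified rank ANCOVA when strata and baseline are modestly prognostic. The attribution problem follows from the text alone. The sizes rest on the assumed R² values, stratum balance and complete data.

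The documents do not support reading this as a threat to the primary conclusion. The conservatism cannot produce a false positive, and the SAP has no rule by which a non-significant rank test overturns the MMRM. The remaining harm is that a true effect may look less robust than it is.

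**What to change.** In SAP 18.1.4 and 18.2.4, replace the rank-sum test with a rank ANCOVA stratified by sex x IBS subtype. Rank change and baseline within each stratum, regress the ranks of change on the ranks of baseline, and apply the CMH mean-score test to the residuals with the same strata. At minimum, use the van Elteren test with those strata; this restores the level but does not use baseline as a covariate. If an estimate is wanted, report a stratified Hodges-Lehmann shift.

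The cost is SAP wording and a few lines of code, plus about 1-3 power points if neither strata nor baseline is prognostic. The LTE SAP (4.3) indicates that the Main Study analysis has since been completed. For this trial the replacement would therefore now be a post hoc analysis, to be labelled as such in the study report under SAP 5.2.

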#### 18.1.5. SUPPLEMENTARY ANALYSIS OF PRIMARY EFFICACY VARIABLE

All analyses described in Sections 18.1.3 and 18.1.4 will be repeated using the Per Protocol Set.

#### 18.2. SECONDARY EFFICACY

#### 18.2.1. SECONDARY EFFICACY VARIABLES & DERIVATIONS

The secondary efficacy analyses will be performed for the FAS. The secondary efficacy endpoints are:

- The proportion of subjects achieving a ≥ 30% improvement in AAPS from baseline to Week 12
- The proportion of subjects achieving a  $\geq$  30% improvement in AAPS from baseline for at

least 6 of the 12 weeks during the Treatment Period

- The proportion of subjects achieving a ≥ 40% improvement in AAPS from baseline to Week 12
- The proportion of subjects achieving a ≥ 40% improvement in AAPS from baseline for at least 6 of the 12 weeks during the Treatment Period
- The proportion of subjects achieving a ≥ 50% improvement in AAPS from baseline to Week 12
- The proportion of subjects achieving a ≥ 50% improvement in AAPS from baseline for at least 6 of the 12 weeks during the Treatment Period
- Percent change in AAPS from baseline to Week 12
- Change in number of pain free days per week from baseline to Week 12

The secondary variables will be derived from the information recorded on the Daily Diary.

Baseline and post-baseline AAPS are calculated as described in Section 7.2.

#### 18.2.2. MISSING DATA METHODS FOR SECONDARY EFFICACY VARIABLES

For the continuous endpoint of percent change in AAPS from baseline to Week 12, the MMRM models described in Section 18.1.3 will be used. For the continuous endpoint of change in number of pain free days per week from baseline to Week 12, the by-week MMRM model described in Section 18.1.3 will be used. For the change in number of pain free days per week endpoint, a subject with a missing value for a given day when there are non-missing values during the week will be assumed to not be pain free for that day.

For the binary endpoints of proportion of subjects achieving a  $\geq$  30% improvement in AAPS from baseline to Week 12 and proportion of subjects achieving a  $\geq$  30% improvement in AAPS from baseline for at least 6 of the 12 weeks during the Main Study treatment period, all missing post-baseline AAPS values will be imputed using MI under the MAR assumption as described in Steps 1 and 2 of Section 18.1.4. The following steps will then follow:

- Step 3: Subjects will be classified as responders or non-responders per imputed data based on the endpoint criteria specified in Section 18.2.1 for the endpoint of interest. For each dataset, the proportion of responders and non-responders will be calculated.
- Step 4: The Cochran-Mantel-Haenszel (CMH) test, stratified by sex and IBS subtype, will be run for each of the 100 datasets to obtain 100 odds ratio estimates of interest (active treatment over placebo). Common risk difference estimates, CIs, and two-sided p-values will also be calculated for active treatment minus placebo based on

Mantel-Haenszel weights. For the 100 odds ratio estimates and difference estimates in each treatment, the estimates will be passed directly to PROC MIANALYZE, along with their associated standard errors. In some cases, an odds ratio estimate may be calculated as missing due to a value of zero in the denominator for certain treatment comparisons; the missing value for that imputation cannot be passed to PROC MIANALYZE. As a result there may be fewer than 100 odds ratio estimates used to calculate the pooled estimate in these instances.

 Step 5: SAS PROC MIANALYZE will be used to produce an overall pooled estimate (mean of 100 estimates) of the odds ratio with associated CI, and of the percentage difference estimate with associated standard error, CI, and two-sided pooled p-values. Counts and percentages of responders will also be summarized using SAS PROC MIANALYZE.

The MI model will be pre-defined before database lock. However, there could be certain adjustments due to unexpected data issues after unblinding treatment. All post-unblinding modifications to the MI model or approaches to address missing data will be described in the CSR.

The robustness of the secondary endpoint results will be assessed using various sensitivity analyses, described in Section 18.2.4.

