#### 9.4. MULTIPLE COMPARISONS/ MULTIPLICITY

No formal testing strategy or adjustments of the type I error will be employed for the primary, secondary or exploratory endpoints. Estimates and CIs for treatment groups and from pairwise comparisons will be used in an exploratory manner.

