#### 18.2.3. ANALYSIS OF SECONDARY EFFICACY VARIABLES

For the continuous secondary efficacy endpoints, percent change in AAPS from baseline to Week 12 and change in number of pain free days per week from baseline to Week 12, the same methodology used for the primary efficacy endpoint will be used for the analysis. The analyses for percent change in AAPS from baseline at Week 12 will include both evaluation at the scheduled visit for Week 12 (Visit 8) and Week 12 based on baseline day as described in Section 18.1.3. The analyses for change in number of pain free days per week from baseline at Week 12 above will include the evaluation at Week 12 based on baseline day as described in Section 18.1.3.

For the binary secondary efficacy endpoints (proportion of subjects with a  $\geq$  30%,  $\geq$  40%, and  $\geq$  50% improvement in AAPS from baseline to Week 12 and proportion of subjects achieving a  $\geq$  30%,  $\geq$  40%, and  $\geq$  50% improvement in AAPS from baseline for at least 6 of the 12 weeks during the Main Study Treatment Period), a CMH test will be conducted to compare placebo against each of the olorinab treatments (10 mg, 25 mg, 50 mg, pooled 25 and 50 mg, and olorinab pooled), stratified by the randomization factor (sex and IBS

subtype). The responder rate and the odds ratio relative to placebo will be presented with corresponding CIs, and the percentage of difference from placebo will be presented together with corresponding 95% CIs and the p-values. The 95% CI for the responder rate of each treatment group will be generated using the normal approximation method. Missing data will be imputed using MI, as described in Section 18.2.2.

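### Responder odds ratios are pooled on the raw scale, so their confidence intervals sit too low and can include 1 beside a clearly significant responder difference

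*SAP*

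**What the plan says.** SAP 18.2.2 imputes missing AAPS, classifies responders in each of 100 datasets, and runs a CMH analysis stratified by sex and IBS subtype in each, giving an odds ratio (active over placebo) and a Mantel-Haenszel risk difference. Step 4 then handles both measures in one sentence: "For the 100 odds ratio estimates and difference estimates in each treatment, the estimates will be passed directly to PROC MIANALYZE", with their standard errors. Step 5 reports "an overall pooled estimate (mean of 100 estimates) of the odds ratio with associated CI". The standard error of the odds ratio is not defined, and neither a log transform nor a back-transform appears in the visible text.

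SAP 18.2.3 has the CMH analysis "compare placebo against each of the olorinab treatments (10 mg, 25 mg, 50 mg, pooled 25 and 50 mg, and olorinab pooled"). It covers three response thresholds (30%, 40%, 50%), each at Week 12 and for at least 6 of 12 weeks, and adds: "Missing data will be imputed using MI, as described in Section 18.2.2". Six endpoints by five contrasts gives 30 odds ratios with CIs. Beside each stands the responder difference with its CI and p-value.

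**The concern.** Pooling by Rubin's rules yields estimate ± t × SE, which is symmetric. That suits a risk difference. The sampling distribution of an odds ratio from 60 v 60, or even 180 v 60, is right-skewed, which is why its interval is normally built on the log scale.

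Three things are at stake. A responder table could show a highly significant difference beside an odds-ratio CI that includes 1. The interval's message would depend on which arm is the numerator. And SAP 18.2.4 says that for binary endpoints "the sensitivity to missing data assumptions will be evaluated with the following models": CMH on observed cases and CMH with non-responder imputation, neither of which needs pooling. If those report the usual log-scale CIs (an assumption), a change of scale would look like sensitivity to missing data.

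**Working it through.** **Inputs.** From SAP section 8: 60 subjects per arm, 180 v 60 for all olorinab against placebo, SD 1.9, effect 1.0. From SAP 7.5: 95% two-sided CIs. The plan gives no responder rates and no responder power, so rates are assumed. Its pairwise power figure reproduces: 60 per arm, 1.0 and 1.9 give 81.6% by noncentral t, against a stated minimum of 80%.

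**Formulas (no missing data).**
- SE(log OR) = √[1/(n₁p₁q₁) + 1/(n₀p₀q₀)]
- Raw-scale CI, delta-method SE: OR × (1 ± 1.96·SE)
- Log-scale CI: OR × exp(± 1.96·SE)

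Because exp(x) ≥ 1 + x for every x, both raw limits lie below their log-scale counterparts at any odds ratio.

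**Worked case, 60% v 30%, 60 per arm.** OR = (0.6/0.4)/(0.3/0.7) = 3.50. SE = √(1/14.4 + 1/12.6) = 0.386, so 1.96·SE = 0.756.
- Raw: 3.50 × (1 ± 0.756) = 0.85 to 6.15
- Log: 3.50 × exp(± 0.756) = 1.64 to 7.45
- Difference: 0.30, SE √(0.24/60 + 0.21/60) = 0.0866, CI 0.13 to 0.47, p = 0.0005
- Inverted (placebo over active): OR 0.286, raw CI 0.286 × (1 ± 0.756) = 0.07 to 0.50. The same data now exclude 1.

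**Other assumed rates.**

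| Active v placebo n | Rates, placebo v active | OR | Raw CI | Log CI | Difference p |
|---|---|---|---|---|---|
| 60 v 60 | 30% v 50% | 2.33 | 0.59–4.08 | 1.10–4.93 | 0.022 |
| 60 v 60 | 30% v 55% | 2.85 | 0.71–4.99 | 1.35–6.04 | 0.004 |
| 120 v 60 | 30% v 50% | 2.33 | 0.80–3.87 | 1.21–4.51 | 0.007 |
| 180 v 60 | 30% v 50% | 2.33 | 0.88–3.79 | 1.25–4.36 | 0.004 |
| 180 v 60 | 35% v 60% | 2.79 | 1.09–4.48 | 1.52–5.12 | 0.0005 |

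With 30% on placebo, the raw CI first excludes 1 at an active rate of about 65% (60 v 60), 56% (120 v 60) or 53% (180 v 60).

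**The other reading of the standard error.** If SE(log OR) were paired with the raw odds ratio, the 60% v 30% case gives 3.50 ± 1.96 × 0.386 = 2.74 to 4.26, far too narrow.

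**Simulation with imputation.** 4,000 trials per setting, 100 imputations, strata of 21/21/9/9 per arm (assumed), Mantel-Haenszel OR with Robins-Breslow-Greenland variance, Rubin's rules with a t reference. Missing outcomes were imputed as binary within arm, which is simpler than the SAP's model. The four effects were 35 v 55%, 35 v 60%, 30 v 60% and 20 v 40%. The table gives the share of trials with a significant difference in which the raw CI excludes 1:

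| Contrast | 0% missing | 5% | 15% |
|---|---|---|---|
| Single dose | 0.1–25% | 0–12% | 0–0.4% |
| 25 + 50 mg pooled | 4–75% | 1.5–66% | 0.1–40% |
| All olorinab | 8–85% | 4–80% | 0.2–65% |

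On the log scale the share was 94–100% throughout. Raw coverage was 92.4–94.3%, with essentially all misses above the upper limit; log coverage was 94.6–96.0%. With no effect (35 v 35%), the raw CI lay wholly below 1 in 5.7–7.2% of trials and wholly above 1 in 0.0%; on the log scale it was 1.9–2.9% on each side. The median odds ratio differed by at most 0.04.

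A separate simulation (30 v 50%, 15% missing, 1,000 trials) agrees. Among trials with a significant difference, the raw CI included 1 in all at 60 v 60, 94% at 120 v 60 and 88% at 180 v 60.

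**The case against.** The strongest case concerns weight. These are secondary endpoints in a Phase 2 study without multiplicity control. The responder p-value belongs to the difference, the success rule in SAP 18.1.3 uses only the AAPS models, and the raw interval does not produce false claims for olorinab. All of that stands and limits the harm. But SAP 9.4 says "Estimates and CIs for treatment groups and from pairwise comparisons will be used in an exploratory manner", so the intervals are what the reader is meant to use, and near-nominal coverage hides misses that are almost all on one side.

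The example SAS code is not visible and may take logs. If so, the text contradicts the code and needs correcting anyway. The reading with mismatched standard errors is conjecture; the natural reading is the delta-method one, and the conclusion does not need the other.

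The 30% v 60% case exceeds the design effect: treating response as a fixed cut on a normal change score with SD 1.9, it implies a shift of 1.48 points. At the planned 1.0 point, 30% on placebo becomes about 50% on active. The raw CI is then 0.59 to 4.09 with p = 0.022, so the conflict is less stark but remains.

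The simulated imputation ignores earlier weeks, which the SAP's model uses. Adding a predictor correlated 0.8 with Week 12 (assumed), at 30 v 60% with 15% missing, moved the share excluding 1 from 0.3% to 3.8% (60 v 60), 39% to 55% (120 v 60) and 66% to 74% (180 v 60). The missing-data columns are therefore pessimistic; the direction holds.

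The SAP fixes the numerator as active, so the inversion demonstrates incoherence and would not itself appear in a table.

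**Conclusion.** The concern holds and should be fixed. As written, the rule gives odds-ratio intervals that are displaced downward. For a single dose at 60 per arm, an effective drug would usually show an odds-ratio CI including 1 next to a significant responder difference. The dose-pooled contrasts are affected less and can escape at large effects. The closed-form sizes rest on assumed responder rates and the delta-method standard error; the simulated sizes also rest on assumed missingness, strata shares and a simplified imputation model. The risk difference, its CI and p-value, and the primary endpoint are untouched, and the point estimate barely moves.

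**What to change.** In SAP 18.2.2, Step 4, define the standard error as that of the log odds ratio and pass log(OR) with SE(log OR) to PROC MIANALYZE. In Step 5, exponentiate the pooled estimate and both limits, and describe the odds ratio as the exponentiated mean of the log odds ratios. Leave the risk-difference pooling as it is. If the programmed code already does this, correct the text to match.

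The cost is two SAP sentences and one data step. The reported odds ratio becomes a geometric rather than arithmetic mean, a change of at most 0.04 in the simulated settings. In the 30% v 60% case the interval becomes 1.64 to 7.45, in agreement with p = 0.0005.
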